9.2 SAMPLE SIZE DETERMINATION

Sample size calculations for this pilot study were based on the two-sample t-test assuming equal variances with a two-sided alpha of 0.05 and a 2:1 (unequal) allocation of subjects NR: placebo. A previous in-vitro study (unpublished to data) yields data for IL-17 levels (pg/ml) for T-cells extracted from psoriatic subjects at baseline and after 72 hours of exposure to 0.5 mM nicotinamide riboside (NR). The observed mean change in IL-17 cytokine release was 329 pg/ml (from 600 to 271 pg/ml) with a standard deviation of 185.74 for the 72-hour changes. For the proposed in-vivo study, we assume a similar change in mean IL-17 (and standard deviation) for psoriatic subjects treated with NR for 4 weeks. For the control subjects receiving placebo, we assume a mean baseline to 4 weeks change in IL-17 of 0 and an equal standard deviation of 185.74 for the 4-week changes.

In the table below, we present power calculations for various scenarios. With 18 subjects on NR and 9 on placebo, the study will have 98% power to detect a difference of 329 pg/ml in the mean baseline to 4-week changes between the two study groups (scenario 1). Note that there will still be 82% power to detect a smaller mean difference of 229 pg/ml between the two study arms (a 100 pg/ml difference less than that achieved in the in-vitro study) should the control subjects exhibit up to a 100 pg/ml decrease in IL-17 due to a placebo effect (scenario 2). Furthermore, even with a loss to follow-up of 3 subjects (2 in the NR arm, 1 on placebo), the study will have 97% power to detect a mean change of 329 pg/ml (scenario 3), and a reduced power just under 80% for a strong placebo effect with a mean difference = 229 pg/ml (scenario 4). Therefore, we request approval to screen up to a total of 40 subjects to account for possible treatment non- compliance and/or study dropouts (18 NR + 9 placebo completing study) and to achieve the objectives of this pilot study.

Scenario	1	2	3	4
#Subjects treated with NR	18	18	16	16
# subjects on placebo	9	9	8	8
Difference in means	329	229	329	229
Power	98%	82%	97%	77%

Abbreviated Title: NR in psoriasis

Version Date: 07/21/2023

9.3 POPULATIONS FOR ANALYSES

N/A

9.3.1 Evaluable for toxicity

All patients will be evaluable for toxicity from the time of their first treatment with study supplement or placebo.

9.3.2 Evaluable for objective response

N/A

9.4 STATISTICAL ANALYSES

9.4.1 General Approach

9.4.2 Analysis of the Primary Endpoints

The primary outcome will be the change in the T_H17 cell cytokine IL-17 secretion in response to T-cell differentiation comparing baseline levels versus their respective response to NR or placebo. The comparisons will be performed using paired two-tailed Student t-tests or if the data is not normally distributed, by the Wilcoxon test. Significance will be tested at the 0.05 alpha level in this pilot study.

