1 PROTOCOL SUMMARY

1.1 SYNOPSIS

Title:	Pilot Study to Evaluate the Effect of Nicotinamide Riboside on Immune Activation in Psoriasis
Study Description:	Psoriasis is a Th17 linked inflammatory disease and we find that the vitaminB3 analogue nicotinamide riboside (NR) blunts Th1 and Th17 activation in ex-vivo naïve and differentiated T cells from control and psoriasis subjects. These findings supported the proposal of the following hypothesis. Supplementation with NR will blunt systemic immune activation in mild/moderate psoriasis.
Objectives:	
 1) Evaluate the effect of NR on Th17 biology 2) Explore the effect of NR on neutrophils, specifically low-density granulocytes 3) Evaluate whether NR modulates keratinocyte activation in skin lesions in psoriatic subjects 4) Evaluate the effect of NR on HDL regulated reverse cholesterol transport and lipid composition
Endpoints:	The primary outcome will be the change in the Th17 cell cytokine IL-17 secretion in response to T-cell differentiation comparing the baseline versus NR or placebo. The comparisons will be performed using paired two-tailed Student t-tests. Significance will be tested at the 0.05 alpha level in this pilot study.
	Exploratory outcomes are:
	
 1) Evaluate the effect of NR on the T cell transcriptome 2) Explore the effect of NR on low-density granulocytes and neutrophils
Study Population:	Up to 40 male and female subjects of all races between the ages of 18-80 years with mild-moderate psoriasis who live locally will be screened.
Phase:	N/A
Description of Sites/Facilities	Enrollment and study visits will take place at the NIH Clinical Center or via telehealth visits .
Enrolling Participants:	Psoriatic Subjects

Abbreviated Title: NR in psoriasis

Version Date: 07/21/2023

Description of Study Nicotinamide Riboside Chloride 500mg or placebo twice daily by mouth for 28 days.

[figure not shown]
Study Duration: 3 years

Participant Duration: 5-23 weeks

Abbreviated Title: NR in psoriasis

Version Date: 07/21/2023

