4 STUDY DESIGN

4.1 OVERALL DESIGN

This study is a pilot, prospective, two-arm double-blind, placebo-controlled study where subjects immunological profile will be studied at baseline and following 4 weeks of supplementation with NR or placebo. The allocation of NR: placebo will be 2:1. All enrolled subjects will receive NR or placebo and following 4 weeks of supplement or placebo intake, research parameters will be compared to baseline to determine the effects of this intervention.

SCIENTIFIC RATIONALE FOR STUDY DESIGN

This is a pilot study and the number of subjects were chosen to allow us to have sufficient samples to use RNAseq analysis to explore the effects of NR on T cell biology if the primary outcome of the study is confirmed.

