6.3 MEASURES TO MINIMIZE BIAS: RANDOMIZATION AND BLINDING

[name] (BioStatistical Co-Investigator on the study) will devise a randomization code. The code will be employed by the pharmacy to dispense the study pills. The study team will be blinded to the code until enrollment is complete and the assays performed for the primary end point.

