9 STATISTICAL CONSIDERATIONS

9.1 STATISTICAL HYPOTHESIS

Supplementation with NR will blunt systemic immune activation in mild/moderate psoriasis.

Primary Endpoint(s): The primary outcome will be the change in the T_H17 cell cytokine IL-17 secretion in response to T-cell differentiation comparing the baseline to NR response after 28 days.

Exploratory Endpoint(s):

- Evaluate the effect of NR on the T cell transcriptome
- Explore the effect of NR on low-density granulocytes and neutrophils

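### The primary analysis tests each arm against its own baseline, so the randomised NR-versus-placebo comparison that the trial was powered for is not planned

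*Combined protocol and SAP*

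**What the plan says.** Section 4.1 describes a "two-arm double-blind, placebo-controlled study" with 2:1 allocation of NR to placebo. Under section 6.3 the biostatistical co-investigator "will devise a randomization code", which the pharmacy uses to dispense.

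The analysis text does not use that structure:

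- Section 9.4.2 defines the primary contrast as "comparing baseline levels versus their respective response to NR or placebo", and then: "The comparisons will be performed using paired two-tailed Student t-tests or if the data is not normally distributed, by the Wilcoxon test". The level is 0.05.
- The synopsis (1.1) says the same: "The comparisons will be performed using paired two-tailed Student t-tests".
- Section 9.1 states the endpoint as "comparing the baseline to NR response after 28 days" and does not mention placebo. The table in section 3 does likewise.
- Section 4.1 says that the effects of the intervention are determined by comparison with baseline.
- Section 9.4.1 (General Approach) has a heading but no text, and 9.4.3 is marked N/A. ANCOVA appears only in the abbreviation list.

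The sample size section takes a different line: "Sample size calculations for this pilot study were based on the two-sample t-test assuming equal variances". It gives power for a difference between the two groups in mean baseline-to-4-week change, and it allows for the case "should the control subjects exhibit up to a 100 pg/ml decrease in IL-17 due to a placebo effect".

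**The concern.** A paired t-test cannot compare two independent groups of 18 and 9. Read with the wording about each arm's respective response, section 9.4.2 yields two separate within-arm tests. Neither of them estimates the effect of NR relative to placebo.

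A before-after test in the NR arm attributes to NR everything that changed between the two visits. The protocol itself allows for a placebo effect. Disease course, stopping vitamin supplements near baseline (section 5.2) and differences between assay runs are further possibilities, though the documents give no size for them. Removing such shared shifts is what the placebo arm is for.

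The plan also has no rule for turning two p-values into one conclusion. The tempting reading, significant on NR and not on placebo, is not evidence that the arms differ. It is especially weak here, because the placebo arm is half the size and misses real changes more often.

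A false positive would have consequences inside the trial: the design rationale in section 4 makes the RNAseq work depend on the primary outcome being confirmed.

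**Working it through.** **Inputs (section 9.2 unless noted).** SD of the change 185.74 pg/ml in both arms; assumed NR change 329 pg/ml; placebo change 0, or a fall of up to 100 pg/ml; 18 NR and 9 placebo, or 16 and 8 after dropout; two-sided alpha 0.05 (9.2 and 9.4.2). Changes are taken as normal and the arms as independent.

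**Step 1: which test gives the stated power?** For a two-sample t-test with equal variances, SE = SD × √(1/n₁ + 1/n₂), noncentrality = difference / SE, and df = n₁ + n₂ − 2. Power comes from the noncentral t distribution.

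- 18 + 9: SE = 185.74 × √(1/18 + 1/9) = 75.83; df 25; critical t 2.060.
- 16 + 8: SE = 185.74 × √(1/16 + 1/8) = 80.43; df 22; critical t 2.074.

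| Scenario | Difference / SE | Computed power | Stated |
|---|---|---|---|
| 1: 18 + 9, 329 | 4.339 | 98.6% | 98% |
| 2: 18 + 9, 229 | 3.020 | 82.7% | 82% |
| 3: 16 + 8, 329 | 4.091 | 97.4% | 97% |
| 4: 16 + 8, 229 | 2.847 | 77.7% | 77% |

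All four figures reproduce as a between-arm test. The test that is planned for the NR arm is a different one: SE = 185.74 / √18 = 43.78, 329 / 43.78 = 7.515, df 17, power above 99.99%.

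**Step 2: what do the paired tests do if NR is inert but both arms shift?** Here SE = SD / √n and df = n − 1. For NR (n = 18), SE = 43.78 and critical t = 2.110. For placebo (n = 9), SE = 185.74 / 3 = 61.91 and critical t = 2.306. With a shared fall of 100 pg/ml the noncentralities are 100 / 43.78 = 2.284 and 100 / 61.91 = 1.615.

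| Shared fall (pg/ml) | NR paired test significant | Placebo paired test significant | NR significant, placebo not | Between-arm test significant |
|---|---|---|---|---|
| 0 | 5.0% | 5.0% | 4.75% | 5% |
| 50 | 19.0% | 11.0% | 16.9% | 5% |
| 100 | 57.7% | 29.6% | 40.6% | 5% |

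The fourth column is the product of independent probabilities; for 100 pg/ml, 0.577 × (1 − 0.2965) = 0.406. The between-arm test keeps its 5% (2.5% in NR's favour) because a common shift cancels in the difference.

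**Step 3: the same pattern when NR works.** In scenario 2 (NR falls by 329, placebo by 100), the NR test is almost always significant, so the chance of NR significant and placebo not is about 1 − 0.2965 = 70.4%. The between-arm test has 82.7%.

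**The case against.** Section 9.2 does name the between-arm difference as what the study should detect, so the protocol can be called self-contradictory rather than silent. That is fair. But 9.2 is a sample-size section, and an analyst who follows 9.4.2 or the synopsis would run paired tests. A contradiction about the primary analysis also has to be resolved before unblinding.

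The 41% and 70% figures depend on a decision rule that the plan never states. This stands: they describe one likely reading. If the NR test alone decides, the false-positive figures are 19% and 58%, and power at 329 pg/ml is above 99.99%.

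The 58% uses the upper end of a hypothetical placebo effect; the base assumption is no placebo change, and there the NR test has no excess error. This also stands. The result is a range from 5% to 58% over shared falls of 0 to 100 pg/ml, and only the placebo effect is sized in the documents.

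The unqualified Wilcoxon test might mean the rank-sum test. As the alternative to a paired t-test it reads as signed-rank, and on either reading it applies only to non-normal data.

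Pilot status limits how far a result would be carried, but the plan still tests at 0.05 and makes later work depend on the outcome. The placebo arm also still supports blinding, so it is not without use.

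**Conclusion.** The concern holds, and the primary analysis is wrong as written. The comparison that randomisation supports has no planned test, and the power statement describes a test that the analysis section does not contain. With inert NR, the probability of a significant NR result rises from 5% with no shared shift to 19% at 50 pg/ml and 58% at 100 pg/ml, against a constant 5% for the between-arm test. These rates assume normal changes with SD 185.74 in both arms and independent arms. The size of any shared shift is unknown; 100 pg/ml is the protocol's own upper figure for a placebo effect. The mismatch between sections 9.2 and 9.4.2 does not depend on these assumptions. The power calculation itself is correct for the test it names.

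**What to change.** Define one primary test in section 9.4.2: the NR-minus-placebo difference in baseline-to-Day-28 change in IL-17 secretion, by the two-sample t-test of section 9.2, two-sided at 0.05, with the estimate and its 95% CI. If a non-normal alternative is kept, name it as the rank-sum test on the changes and state in advance when it applies. Report the within-arm paired results as descriptive only, with no claim of effect based on them.

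Align the synopsis (1.1), section 3 and section 9.1 with this, and also the sentence in 4.1 on comparison with baseline.

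The cost is wording in these five places, made before unblinding. No subjects, samples or assays are added. Power is then as section 9.2 states: 98.6% for 329 pg/ml and 82.7% for 229 pg/ml at 18 + 9, and 97.4% and 77.7% at 16 + 8. The price to the sponsor is that the NR result may look less significant than it would under the paired test.

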7.2 PARTICIPANT DISCONTINUATION/WITHDRAWAL FROM THE STUDY

Participants are free to withdraw from participation in the study at any time upon request. An investigator may discontinue or withdraw a participant from the study for the following reasons:

- 1) Subject taking less than 75% of their capsules
- 2) Subject found to be pregnant or wishes to breastfeed during the study will automatically be withdrawn
- 3) If subject no longer wish to participate
- 4) Subject's non-compliance or per PI discretion for development of a condition that may independently affects immune activity.

Prior to removal from study, any subject who has started the study intervention should complete a safety visit. For subjects who complete the study, this would be included in Visit 2. If a subject requests withdrawal early for any reason, we will make every effort to have them complete an

Abbreviated Title: NR in psoriasis

Version Date: 07/21/2023

unscheduled safety visit..

The reason for participant discontinuation or withdrawal from the study will be recorded in the source document. Subjects who sign the informed consent form and are randomized but do not receive the study intervention may be replaced. Subjects who sign the informed consent form, and are randomized and receive the study intervention, and subsequently withdraw, or are withdrawn or discontinued from the study, will be replaced until the recruitment goals of 18 NR and 9 placebo subjects have completed the protocol. Participants who are withdrawn for reasons that are temporary, such as an infectious disease or administration of an immunization, may be re-screened and if they meet eligibility then re-enrolled with a new study id.

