8.2.2 Biospecimen Evaluations

Biological specimen collection and laboratory evaluations. In addition to the clinical blood samples, subject will have research bloods drawn within the blood withdrawal volume limits established by the Clinical Center. RNAseq, Flow cytometry, metabolomics, HDL cholesterol uptake and cytokine profiling may be performed. Skin biopsy samples may be obtained for culture or isolation of distinct cell populations for subsequent biochemical, cell biological and molecular analyses and for immune-histochemistry. With the patient's consent, a biopsy each of lesional skin (where there is active psoriasis) and non-lesional sites (where there is no psoriasis) will be performed, and hemostasis will be achieved. The skin biopsy will be performed by a healthcare provider and will be used primarily for research purposes.

Abbreviated Title: NR in psoriasis

Version Date: 07/21/2023

Test/assay	Volume blood (approx.)	Type of tube	Collection point (+/- 48hrs)	Location of specimen analysis
Immune-monitoring	80 mls for PBMC's and NAD+. 20mls for Neutrophils. 20mls for low density granulocytes (LDG's).	Green Tops for PBMC's and NAD+ Green Tops for Neutrophils Green Tops for LDG's	Baseline and 4 weeks.	[name] Lab (Deliver to [name] lab)
HDL reverse transport	5-10mls (for serum)	Red top	Baseline and 4 weeks	[name] lab

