11 ABBREVIATIONS

AE	Adverse Event
ANCOVA	Analysis of Covariance
CFR	Code of Federal Regulations
CLIA	Clinical Laboratory Improvement Amendments
CMP	Clinical Monitoring Plan
COC	Certificate of Confidentiality
CONSORT	Consolidated Standards of Reporting Trials
CRF	Case Report Form
DCC	Data Coordinating Center
DHHS	Department of Health and Human Services
DSMB	Data Safety Monitoring Board
DRE	Disease-Related Event
EC	Ethics Committee
eCRF	Electronic Case Report Forms
FDA	Food and Drug Administration
FDAAA	Food and Drug Administration Amendments Act of 2007
FFR	Federal Financial Report
GCP	Good Clinical Practice
GLP	Good Laboratory Practices
GMP	Good Manufacturing Practices
GWAS	Genome-Wide Association Studies
HIPAA	Health Insurance Portability and Accountability Act
IB	Investigator's Brochure
ICH	International Conference on Harmonisation
ICMJE	International Committee of Medical Journal Editors
IDE	Investigational Device Exemption
IND	Investigational New Drug Application
IRB	Institutional Review Board
ISM	Independent Safety Monitor
ISO	International Organization for Standardization
ITT	Intention-To-Treat
LSMEANS	Least-squares Means
MedDRA	Medical Dictionary for Regulatory Activities
MOP	Manual of Procedures
MSDS	Material Safety Data Sheet
NCT	National Clinical Trial
NIH	National Institutes of Health
NIH IC	NIH Institute or Center
OHRP	Office for Human Research Protections
PI	Principal Investigator
QA	Quality Assurance
QC	Quality Control
SAE	Serious Adverse Event
SAP	Statistical Analysis Plan
SMC	Safety Monitoring Committee
SOA	Schedule of Activities
SOC	System Organ Class
SOP	Standard Operating Procedure
UP	Unanticipated Problem
US	United States

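### Baseline IL-17 is collected but not used as a covariate; naming ANCOVA when the between-arm test is added would be a cheap precision gain, with a caveat on the interval

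*Combined protocol and SAP*

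**What the plan says.** Section 9.4.2 compares baseline with the response to NR or placebo, arm by arm: "The comparisons will be performed using paired two-tailed Student t-tests or if the data is not normally distributed, by the Wilcoxon test". It names no covariate and no NR-versus-placebo test. Section 4.1 describes the same logic: "following 4 weeks of supplement or placebo intake, research parameters will be compared to baseline".

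Section 9.2 rests on a different test, the "two-sample t-test assuming equal variances with a two-sided alpha of 0.05", applied to the baseline-to-4-week changes. It takes the NR arm's SD of change from in-vitro data and gives the placebo arm "an equal standard deviation of 185.74 for the 4-week changes". For its scenario 2 it states that "there will still be 82% power to detect a smaller mean difference of 229 pg/ml between the two study arms". Baseline does not enter as a covariate here either.

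The baseline value will be available. The Schedule of Activities (1.3) lists PBMC samples at baseline and day 28, and the table in 8.2.2 provides "80 mls for PBMC's and NAD"+ at both time points. Under 7.2, treated participants who leave "will be replaced until the recruitment goals of 18 NR and 9 placebo subjects have completed the protocol", so the planned 18+9 completers should have both values.

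"Analysis of Covariance" appears only in the abbreviation list (section 11).

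**The concern.** The trial aims for 27 completers, nine of them on placebo. A chance difference in baseline IL-17 between such small arms is quite possible. The change score handles it by fixing the slope of day-28 on baseline at 1. ANCOVA estimates that slope from the data. When the true slope is well below 1, as it is when assay and biological variation make the two visits only moderately correlated, ANCOVA gives a narrower interval for the NR–placebo difference from the same blood samples.

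At stake is the precision of the estimated difference, and power where 9.2 has least margin: scenario 2 (82%) and scenario 4 (77%). Whoever adds the missing between-arm test will have to choose its form. A plain two-sample t-test would remove the mismatch between 9.2 and 9.4.2 and still leave baseline unused.

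**Working it through.** **Inputs from section 9.2.** SD of change 185.74 pg/ml in both arms; two-sided alpha 0.05; arms 18+9 (16+8 after dropout); differences of 329 and 229 pg/ml.

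**Inputs not in the documents, so assumed.** The baseline-to-day-28 correlation (rho), and the ratio k of the day-28 SD to the baseline SD.

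**1. The plan's own figures.** The standard error of the difference in mean change is 185.74 × sqrt(1/18 + 1/9) = 75.83. At 229 the noncentrality is 229/75.83 = 3.02, and the noncentral t with 25 df gives 82.7% (stated 82%). The other scenarios give 98.6%, 97.4% and 77.7% (stated 98%, 97% and 77%). All four reproduce. The 95% half-width at 18+9 is 2.06 × 75.83 = 156 pg/ml.

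**2. ANCOVA residual variance.** Relative to the variance of change it is

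k²(1 − rho²) / (1 + k² − 2·rho·k).

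Denominator minus numerator equals (1 − rho·k)², which is never negative. So the residual SD cannot exceed 185.74, and it reaches that value only when the slope rho·k equals 1. With equal visit SDs (k = 1) the ratio is (1 + rho)/2.

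**3. What ANCOVA costs.** One degree of freedom (24 instead of 25), and a variance factor for chance baseline imbalance, 1 + F/25 with F on (1, 25) df, whose mean is 1 + 1/23. Power is averaged over that factor.

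**4. Floor, slope 1.** At 18+9 and 229 pg/ml power is 81.0%, a cost of 82.7 − 81.0 = 1.7 points, of which 0.13 comes from the lost degree of freedom. The half-width is 160. Simulated slope-1 cases gave 80.8–81.4%.

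**5. Elsewhere (18+9, 229 pg/ml).**

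| k | rho 0.2 | rho 0.5 | rho 0.8 |
|---|---|---|---|
| 0.75 | 99.1% | 97.5% | 96.6% |
| 1 | 95.5% | 90.5% | 84.8% |
| 1.25 | 91.4% | 85.1% | 81.0% |

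For k = 1 the half-widths are 124, 138 and 152 pg/ml. ANCOVA gains when its residual SD is below about 182 pg/ml. With k = 1 that means rho below about 0.91. With k = 1.25 there is a loss between rho of about 0.63 and 0.90.

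**6. Other scenarios.** At 329 pg/ml and 18+9: 98.6% unadjusted, 98.2% at the floor, 99.0–99.9% with k = 1 and rho from 0.8 to 0.2. At 16+8 and 229 pg/ml: 77.7% unadjusted, 75.6% at the floor, and 92.7%, 86.4% or 79.8% with k = 1 and rho 0.2, 0.5 or 0.8.

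**7. If NR lowers IL-17 proportionally.** The NR arm's day-28 values then spread less than the placebo arm's, and the smaller arm has the larger variance. Simulation used lognormal data with mean 600, equal pre-treatment visit SDs, SD of change 185.74 before any effect, rho 0.2 to 0.8, and 40,000 trials per setting. Coverage of nominal 95% intervals:

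| Interval | 600 to 371 | 600 to 271 |
|---|---|---|
| ANCOVA, raw scale, pooled variance | 90–91% | 86–88% |
| ANCOVA, raw scale, HC3 | about 94–95% | about 92–94% |
| ANCOVA, log scale | about 95% | about 95% |
| Change score | about 94% | about 93–95% |

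With no effect, pooled ANCOVA keeps its type I error at about 5%.

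**8. If HC3 is used for the test.** In the slope-1 cases (rho 0.8, k 1.25; rho 0.5, k 2) power at 229 pg/ml is 76–77%, about 6 points below the change score.

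**The case against.** The strongest reply is that nothing here is wrong. A change score is a legitimate analysis, this is a pilot, and the larger fault in 9.4.2 is that it contains no between-arm comparison at all; baseline adjustment could be one line in that repair. This stands as to weight and order: the adjustment has no role until a between-arm test exists. It does not remove the point, because the form of that test still has to be chosen.

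Second, the gain rests on values the protocol does not report. That stands. A reader might infer a gain of 2 to 13 points, but that range needs equal SDs at the two visits. The equal variances in 9.2 are those of the two arms, and no visit SD is given.

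Third, a reader might take 1.7 points as an unconditional ceiling on the cost. It is not. It holds for the pooled-variance test, with equal arm variances, as an average over randomisations. A realised imbalance of t = 2 with no help from the covariate gives about 76.7%. Under a proportional effect the raw-scale pooled interval also loses coverage, most at the planning case itself. This part of the objection is right, and it changes the fix.

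Last, the ANCOVA entry in section 11 might suggest an intended analysis that was dropped. The list also carries GWAS and LSMEANS, which the plan never uses, so it shows nothing about intent.

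**Conclusion.** The point holds as a recommended refinement. Sections 9.2 and 9.4.2 leave a collected baseline measurement unused. The omission causes no bias, and the documents do not support calling it an error.

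In the 229 pg/ml scenario the expected power cost of adjusting is small. The possible gain is larger, but its size and, in a limited region near slope 1, its sign depend on rho and k, which are assumptions. At the main design difference of 329 pg/ml there is almost no power to gain, and the benefit is a narrower interval where the slope is well below 1.

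The power figures assume normal data, a common slope and equal arm variances. If NR acts proportionally, the scale and the standard error matter as much as the covariate. Confidence is medium for that reason.

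**What to change.** When the between-arm test is added to 9.4.2:

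- Prespecify it as ANCOVA of day-28 IL-17 on treatment, with baseline IL-17 as covariate.
- Name the model and the scale (raw or log) before the randomisation code described in 6.3 is opened.
- On the raw scale, report the adjusted NR–placebo difference with an HC3 95% interval beside the pooled one. If a proportional effect is expected, use the log scale.
- Name one rank-based sensitivity test.

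The change is wording only, with no new samples or participants. The downsides to state in the plan are one residual degree of freedom; up to 1.7 power points for the pooled test under the conditions above, and more if HC3 is used for the test; and, under a proportional effect, undercoverage of the raw-scale pooled interval, which HC3 largely but not fully repairs.
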